## 8.13 Handling of Missing Adverse Event Severity and Relationship

If Severity is missing the event will be assumed to be severe. If relationship is missing the event will be assumed to be the most related, i.e. probably related.

## 8.14 Imputation of Titers Below the Limit of Quantification (BLQ)

The Lower Limit of Quantification (LLOQ) will be provided in the immunogenicity vendor data transfer. For titers BLQ the reported result of the LLOQ will be replaced with an imputed value of half the LLOQ, i.e. 0.5\*LLOQ. Listings will include the original result as provided by the vendor.

## 8.15 Imputation of Biomarker Values Below the Limit of Quantification (BLQ)

The Lower Limit of Quantification (LLOQ) will be provided in the biomarker vendor data transfers. For values BLQ the reported result will be replaced with an imputed value of the LLOQ. Listings will include the original result as provided by the vendor.

## 8.16 Geometric Mean Titer

The Geometric Mean Titer (GMT) is calculated by taking the antilogarithm of the mean of the log10 transformed titers. Antibody titers BLQ will be imputed as outlined in Section 8.14.

# 8.17 Normal Approximation Confidence Interval (CI) for the Geometric Mean Titer

Lower Limit=antilogarithm of LL, where LL = Mean of log values – 1.96 x Standard Error of log values.

Upper Limit=antilogarithm of UL, where UL = Mean of log values + 1.96 x Standard Error of log values,

where the Standard Error of log transformed values is the Standard Deviation (calculated on log transformed data) divided by the square root of the number of observations.

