3.5.2.8 Visit 4.1 [Week 15]

This visit is only applicable in future sub-cohorts or in ongoing sub-cohorts, in subjects not having yet reached this visit timepoint. If feasible, agreed with subject and locally permitted, these visits may also be performed at subject's home.

- AEs

- Concomitant medications (describe new and/or changes from the previous visit)
- Blood samples collected for:

antibody response components including for example anti-pTau and anti-Tau IgG and IgM titers

AD biomarker assessment

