5.3.4 Demographic and Baseline Characteristics

Dose groups will be compared with respect to subject demographics and baseline characteristics will be summarized using descriptive statistics. No formal statistical analysis tests will be performed.

Placebo subjects can be pooled over different (sub-)cohorts for presentation, where appropriate.

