#### Sub-cohort expansion

Optional sub-cohort expansion of up to 16 additional subjects (i.e. up to 12 on active treatment and up to 4 on placebo per sub-cohort) may be considered in sub-cohort(s) with a favorable safety and immunogenicity profile with the objective to confirm the initial sub-cohort(s) immunogenicity results. The number of additional subjects to be enrolled will be determined based on the observed immunogenicity response rate in the sub-cohort(s) and on the potential gain in precision of the response rate estimate in the expanded sub-cohort(s), and will not exceed 16 (i.e., up to 24 subjects overall per sub-cohort). In addition, all other immunogenicity endpoints available at the interim timepoint may be considered. The dose-level, sequence of administration and administration regimen of study vaccine(s) will be identical to the initial part of the sub-cohort.

**Note:** An expansion of 17 additional subjects was done in sub-cohort 1.2 (for a total of 25 subjects in that sub-cohort) to allow further assessment of safety and immunogenicity at that dose. It was considered that the recruitment of 17 (instead of up to 16 as planned per protocol) subjects is acceptable by the Sponsor.

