## 6.1 Sample Size Considerations

Antibody titer assessment: The preliminary assessment of the antibody response and of the safety/tolerability (comparison between sub-cohorts) will be performed based on the data of all randomized subjects (6 on ACI-35.030/JACI-35.054 and 2 on placebo per sub-cohort) based on the timepoints related to the different IAs that will be conducted during the study. The initial number of subjects in each sub-cohort is consistent with the customary sample size employed in this type of studies. It is expected to allow clinical judgement of safety and tolerability, and to get preliminary evidence of an acceptable immune response. This sample size is also anticipated to provide sufficient evidence to support the possible enrollment of up to 16 additional subjects in the sub-cohort(s) showing the most favorable antibody response profile(s) with the objective to confirm the initial results. The number of additional subjects to be enrolled will be determined based on the preliminary observed immunogenicity response rate in the subcohort(s), and on the potential gain in precision of the response rate estimate in the expanded sub-cohort(s), and will not exceed 16 (12 on ACI-35.030/JACI-35.054 and 4 on placebo per sub-cohort). In addition, all other immunogenicity endpoints available at the interim timepoint may be considered in the sample size re-estimation. This may include but is not limited to the observed variability of titers such as the Anti-pTau IgG and the Anti-e-PHF IgG.

In total, up to 24 subjects can be randomized to cohort 1, cohort 2 and cohort 3, respectively (not taking into account sub-cohort(s) expansion). Any randomized subject withdrawing before the 2nd injection for reasons other than safety may be replaced in the cohort.

For safety, if an AE occurs at the rate of 1% or 10%, then the chance of observing such an AE among 6 subjects receiving that dose of active treatment will be 6% or 47%, respectively. If no AE of a given type is observed in any of the 6 subjects at a given dose of active treatment, then with 80% (90%) confidence the true incidence of that type of AE at that dose is at most 24% (32%).

An expansion was done in sub-cohort 1.2 in which 17 additional subjects were recruited (for a total of 25 subject in the sub-cohort) to allow further assessment of safety and immunogenicity at that dose.

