# 11.0 Statistical Methods

All analyses will use SAS® version 9.4 or higher. Descriptive summaries will be tabulated by treatment group (ACI 300µg, ACI 900µg, ACI 1800µg, JACI 15µg, JACI 60µg). Where applicable, all subjects from each main cohort will be summarized together (excluding immunogenicity and biomarker TFLs).

Categorical data will be presented using counts and percentages, with the number of subjects in each category as the denominator for percentages. Percentages will be rounded to one decimal place except 100% will be displayed without any decimal places and percentages will not be displayed for zero counts.

Continuous data will be summarized using the number of observations (n), mean, standard deviation (SD), median, first quartile, third quartile, minimum, and maximum. Minimum and maximum will be rounded to the precision of the original data. Mean and median will be rounded to 1 decimal place greater than the precision of the original data. The SD will be rounded to 2 decimal places greater than the precision of the original data, up to a maximum of 3 decimal places.

A sensitivity analysis may be carried out at the end of the study if the number of patients impacted by the COVID-19 pandemic is large (e.g. >10% missed injections due to COVID-19) and thought to be impacting the efficacy and safety endpoints. This sensitivity analysis may exclude the patients affected by the pandemic.

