#### **11.6.1 Immune Response for Primary Endpoints**

Descriptive statistics of actual values and changes from baseline as outlined in section 11.0, with the addition of Geometric Mean and 95% normal approximation confidence intervals (CI) as outlined in sections 8.15 and 8.17, will be presented for the primary immune response variable, anti-pTau IgG and anti-ePHF IgG titers in serum by Visit [Baseline, Visit 2 (Week 2), Visit 3 (Week 8), Visit 4 (Week 10), Visit 4.1 (Week 15), Visit 4.2 (Week 20), Visit 5 (Week 24), Visit 6 (Week 26), Visit 6.1 (Week 31), Visit 7 (Week 36), Visit 7.1 (Week 42), Visit 8 (Week 48), Visit 9 (Week 50), Follow-up Visit 10 (Week 67) and Follow-up Visit 11 (Week 74)] and Treatment Group [TFL Shell Table 14.2.1.1, 14.2.1.1.1; 14.2.5.1, 14.2.5.1.1]. This variable will further be summarized by Treatment Group for responder rate [TFL Shell Table 14.2.1.2, 14.2.1.2.1; 14.2.5.2, 14.2.5.2.1], and area under the curve and peak [TFL Shell Table 14.2.1.3, 14.2.1.3.1; 14.2.5.3, 14.2.5.3.1] by Treatment Group (and overall for baseline data only) in the Intention-to-Treat Population.

The time-dependent development of the geometric mean titers will be displayed graphically per Treatment Group for the actual values as well as for change from baseline [TFL Shell Figure 14.1.1.1, 14.1.1.1.2; 14.1.5.1, 14.1.5.1.1, 14.1.5.1.2] and by subject [TFL Shell Figure 14.1.1.2, 14.1.5.2]. Boxplot of the actual value summarized by Visit and Treatment Group will also be prepared [TFL Shell Figure 14.1.1.4 and 14.1.5.4].

Response rates by Visit will be displayed graphically in a response rate verses dose plot to investigate whether there is any dose response relationship [TFL Shell Figure 14.1.1.3; 14.1.5.3].

No statistical testing has been planned for antibody responses.

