## 12.0 Changes from the Analysis Planned in the Protocol

Due to the COVID-19 pandemic a notification of an Urgent Safety Measure (USM) for a change to protocol study procedures, effective immediately, was submitted to FIMEA on **01-Apr-2020** and Finnish EC (TUKIJA) on **03-Apr-2020**. A protocol amendment following the USM including the below changes was submitted to FIMEA on **17-Apr-2020** and TUKIJA on **24-Apr-2020**:

- Replacement of Visit 5 (Week 24) and Visit 6 (Week 26) by remote visits in 7 of 8 Sub-cohort 1.1 subjects. As a consequence, the third immunization, as well as procedures and assessments requiring the subjects to travel at Visit 5 (Week 24) and Visit 6 (Week 26) were cancelled.
- Cancellation of the third phone call (P3), usually performed 48-72 hours after the third immunization. This change is impacting 7 of 8 subjects who have not had their immunization at Visit 5 (Week 24) prior to the at-risk period.

Due to the changes presented above IA #2 Sub-cohort 1.1 at Week 50 will be executed as follows:

- Individual data (listings and individual figures) will not be presented for IA #2 Sub-cohort 1.1 Week 50.
- Aggregate data (summary tables and figures) will be provided for all timepoints (up to Week 50) except the timepoints where the visits were missed by 7 of 8 subjects in Sub-cohort 1.1 for which we will have only 1 value (i.e. Visit 5 Week 24 and Visit 6 Week 26).

Footnotes will be included to all outputs affected by the selection criteria as given below:

• Aggregate data outputs: "Note: Aggregate data is provided for all visits except those missed by 7 out of 8 subjects in Sub-cohort 1.1 (Visits 5 and 6)."

In certain cases, where subjects missed any visit or dropped out from the study, IA will be executed as follows:

[figure not shown]
- If there is a risk of unblinding individual data (listings and individual figures) will be presented only up until the missed visit or data for those subjects will not be included.
- Aggregate data (summary tables and figures) will be provided for all timepoints

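### The 95% interval for the geometric mean titer uses 1.96 instead of the t quantile, so with 6 subjects per group it covers about 89%

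*SAP*

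**What the plan says.** SAP 8.16 defines the geometric mean titer as the back-transformed mean of log10 titers. SAP 8.17 then gives the interval: "Upper Limit=antilogarithm of UL, where UL = Mean of log values + 1.96 x Standard Error of log values", with the mirror image for the lower limit. The standard error is the SD of the log values divided by the square root of the number of observations. The multiplier does not depend on n.

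SAP 11.6.1 applies this to the primary titers, "with the addition of Geometric Mean and 95% normal approximation confidence intervals (CI", by visit and treatment group. SAP 11.6.2 and 11.6.3 present the secondary and exploratory titers in the same way. SAP 11.6.1 also says that no statistical testing of antibody responses is planned.

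On group size, SAP 6.1 states "6 on ACI-35.030/JACI-35.054 and 2 on placebo per sub-cohort". Under SAP 11.0, "Descriptive summaries will be tabulated by treatment group", and five active groups are listed: ACI 300, 900 and 1800 µg, and JACI 15 and 60 µg. Only the 900 µg group was enlarged: "An expansion of 17 additional subjects was done in sub-cohort 1.2 (for a total of 25 subjects in that sub-cohort". SAP 6.0 notes that sub-cohort 2.3 and cohort 3 were never started. Neither document gives a small-sample correction or a minimum n for the interval.

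**The concern.** The value 1.96 is right when the SD is known or n is large. Here the SD is estimated from about 6 values, and the uncertainty in that estimate has to go into the multiplier. Leaving it out makes the interval too short for its label.

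With no testing planned, the geometric means and their intervals are the main statement of precision for the primary immunogenicity endpoint. They will also be read across groups: Protocol 1.4 says the primary endpoints are the basis for choosing the vaccine with the best profile, and Protocol 1.2 says the regimens will be compared to choose a strategy. The shortfall is uneven. It is largest in the four small groups and small in the expanded one, so the small groups look more precise relative to the 900 µg group than they are.

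The number of values at a visit can also fall below 6. Of the added Visit 4.1, Protocol 3.5.2.8 says "This visit is only applicable in future sub-cohorts or in ongoing sub-cohorts, in subjects not having yet reached this visit timepoint", and the same condition applies to Visits 4.2, 6.1 and 7.1.

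**Working it through.** **Inputs**
- Nominal level: 95%, two-sided (SAP 11.6.1).
- Multiplier: 1.96. Standard error: SD of logs / √n, with the sample SD (SAP 8.17).
- n = 6 active in each of sub-cohorts 1.1 (300 µg), 1.3 (1800 µg), 2.1 (15 µg) and 2.2 (60 µg) (SAP 6.0). It is about 6 because early withdrawals may be replaced.
- 900 µg group: 25 subjects including placebo. The active count is not stated. At the 3:1 ratio, 25 × 0.75 = 18.75, so 18 or 19 is assumed.

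**Reproducing the plan's own figures.** The normal 0.975 quantile is 1.95996, so 1.96 is the correct large-sample value. The planning size of 6 is confirmed by the safety figures in SAP 6.1:
- 1 − 0.99^6 = 5.9% (stated 6%)
- 1 − 0.9^6 = 46.9% (stated 47%)
- 1 − 0.2^(1/6) = 23.5% (stated 24%)
- 1 − 0.1^(1/6) = 31.9% (stated 32%)

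**Coverage.** With normal log titers and an estimated SD, coverage of mean ± 1.96 × SE is 2·T(1.96; n − 1) − 1, where T is the t distribution function. It does not depend on the true SD.

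| n | coverage with 1.96 | t(0.975, n − 1) | t / 1.96 |
|---|---|---|---|
| 4 | 85.5% | 3.182 | 1.62 |
| 5 | 87.8% | 2.776 | 1.42 |
| 6 | 89.3% | 2.571 | 1.31 |
| 18 | 93.3% | 2.110 | 1.08 |
| 19 | 93.4% | 2.101 | 1.07 |

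At n = 6, non-coverage is 100 − 89.3 = 10.7%, about twice the nominal 5%. The planned interval is 1 − 1.96/2.571 = 24% too short on the log scale; put the other way, the t interval is 31% wider. A simulation of 1,000,000 normal samples of 6 gave 89.3% with 1.96 and 95.0% with t.

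**On the titer scale.** The limits are GMT multiplied and divided by 10^(k × SD/√6), with k = 1.96 or 2.571. The documents give no SD for log10 titers, so a range is assumed:

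| assumed SD (log10) | factor with 1.96 | factor with t |
|---|---|---|
| 0.2 | 1.45 | 1.62 |
| 0.4 | 2.09 | 2.63 |
| 0.6 | 3.02 | 4.26 |

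**Apparent separation.** For two groups of 6 with the same true mean and SD, simulation gives non-overlapping intervals in 2.2% of cases with 1.96 and 0.5% with t.

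**Placebo.** Placebo is not among the groups listed in SAP 11.0, and Protocol 5.3.4 says only "Placebo subjects can be pooled over different (sub-)cohorts for presentation, where appropriate". Coverage therefore depends on a grouping that is not stated:
- per sub-cohort, n = 2: 70.0%
- pooled within cohort 2, n = 4: 85.5%
- pooled within cohort 1, n = 10 to 11 (2 + 2 + an assumed 6 or 7): 91.8 to 92.2%
- all pooled, n = 14 to 15 (the same assumption): 92.8 to 93.0%

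**The case against.** The strongest reply is that the interval is openly called a normal approximation, is descriptive, and is additional to what the protocol asks for. Protocol 5.3.6.2 lists geometric mean, change from baseline, response rate, peak and AUC, without an interval. No point estimate changes, no expansion rule uses these limits, and the SD, quartiles, range, box plots and individual curves show the spread anyway. That stands, and it limits the harm to stated precision. It does not make the interval a 95% interval at n = 6.

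Second, non-overlap of equal groups at 2.2% is still rarer than a conventional 5% error. This is fair: the planned intervals do not produce frequent false separation. They do produce it about four times as often as correctly built ones (2.2% against 0.5%).

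Third, 89.3% assumes normal log titers. Imputation at half the LLOQ (SAP 8.14) and a mix of responders and non-responders would break that assumption, most clearly for anti-CpG and anti-T50, where every negative sample is reported as below the limit. This is true of both intervals. In an assumed mixture of 20 to 30% non-responders shifted by 1 log10, with within-group SD 0.3 and n = 6, t covers about 92% and the planned interval 86 to 87%. So t does better but does not guarantee 95%.

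Fourth, the sub-cohort 1.1 visits described in SAP 12.0 ("for which we will have only 1 value (i.e. Visit 5 Week 24 and Visit 6 Week 26") are not evidence either way, because with one value no interval exists under either formula. The documents also do not say how far the added visits reduce n in any group.

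**Conclusion.** The concern holds. SAP 8.17 uses a large-sample multiplier with an estimated SD, and SAP 11.6.1 labels the result 95% although four of the five active groups have about 6 subjects. Under roughly normal log titers, actual coverage there is 89.3%, against about 93.3 to 93.4% in the 900 µg group (assuming 18 or 19 active). The headline figure rests only on documented group sizes and the normality assumption. The 900 µg and pooled cohort 1 or all-placebo figures rest on an assumed split of the 17 added subjects, and the titer-scale factors on an assumed SD.

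The consequence is moderate: overstated and uneven precision on a primary endpoint, with the same effect in the secondary and exploratory titer tables. No error rate of a test and no decision threshold is affected. It should be fixed because the correct interval is standard and easy to produce.

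**What to change.** In SAP 8.17, replace 1.96 in both limits with t(0.975, n − 1), where n is the number of observations in that group at that visit. Rename the section as a t-based interval on log10 titers and change the matching description in SAP 11.6.1. Add a sentence that the interval assumes approximately normal log titers and is not exact where many values are imputed at half the LLOQ.

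Two optional additions would help: state in SAP 11.0 how placebo is grouped in the titer tables, since that sets n, and show individual values rather than an interval where n is 1 or 2.

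The cost is a few lines of SAP text and one program option. Because version 4.0 is final and SAP 3.0 requires sponsor approval of non-administrative changes, it also needs a re-approval. The intervals become wider: by 31% on the log scale at n = 6, and by about 7 to 8% at n = 18 to 19. No new data are needed.

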# Avidity will be calculated as a ratio and hence no unit is applicable

\$ Only Post treatment results are reported for anti-ePHF avidity (i.e. Screening and Visit 1 are not applicable) of samples that are positive for anti-ePHF IgG antibodies.

\* ePHF avidity will not be reported if ePHF IgG is negative or if ePHF IgG average of multiple runs is used and ePHF avidity is considered unreportable by the sponsor. In both cases blank result value will be populated, "NVR" (no valid result) will be

included in the Status column and a reason will be added in the comments ("ePHF IgG negative" or "ePHF IgG average of multiple runs").

& determination of positive or negative samples is made by . Numeric values are only reported on samples positive for antibodies. In case the concentrations are undetectable or samples are evaluated as negative, "BLQ" (Below Limit of Quantification) is reported.

For layout/reading purpose, shorter adjuvant names have been used, i.e. CRM in place of CRM197.

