New patient IDs will be programmatically generated and assigned to patients using SAS® by an unblinded statistical programmer at the "RANUNI" function will be used to recode patient IDs and ensure that there is no discernible sequence or pattern, with a seed number that is known to the unblinded statistical programmer and a second unblinded person at the CRO, but unknown to the Sponsor/Blinded Team. Analysis output of antibody titer and biomarker results will be displayed using recoded patient IDs. Hence, the Sponsor will not be able to draw conclusions as to the patients' original IDs.

A list with original patient IDs and associated recoded patient IDs will be generated via SAS®. The list will be maintained by the unblinded statistical programmer and made available to the Sponsor/Blinded Team after study unblinding (following database lock) and filed in the appropriate unblinded section the electronic Trial Master Files (eTMF).

DATA MUST NEVER BE SENT FROM THE ANALYZING LABORATORIES TO AC IMMUNE SA, THE SITE, BLINDED TEAM MEMBERS, PATIENTS AND/OR CAREGIVERS TO AVOID ANY UNBLINDING!

All electronic files and related emails provided by the analyzing laboratories will be maintained by the unblinded team and filed in the unblinded section of the eTMF. Sponsor should not have access to these files before study unblinding (following database lock).

In case there is missing data at one or more visit timepoints for a patient (e.g. in case of early withdrawal from treatment due to safety), the results pertaining to that patient will only be included in the TFLs summarizing the results per dose group and will not be presented individually. This is applicable when producing IA.

All SAS programs created for the study for data recording purposes will be validated according to **Standard Operation Procedures.** No recoding will be done for safety, tolerability and data related to cognitive and clinical effects, as data will be extracted directly from the eCRF.

Additionally, anti-double stranded DNA results (corresponding to the anti-dsDNA ELIA) are blinded to the site investigator due to risk of unblinding, but they must not be blinded to the DSMB and sponsor. Both should receive the results for both anti-dsDNA testing (ELIA and FARR) to allow safety monitoring of the subjects.

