## 7.2 Secondary Endpoints

[figure not shown]
Immunogenicity of study vaccine will be assessed by:

- Examination of the immune response: anti-Tau IgG, anti-pTau IgM and anti-Tau IgM titers in serum (e.g. geometric mean, change from baseline, responder rate, peak and area under the curve)
- Determination of the IgG response profile by avidity testing

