### 8.19 Avidity index

The avidity index will be reported by based on the ratio between the concentration of anti-enriched Paired Helical Filaments [anti-ePHF] IgG measured in saturated (high coating) and unsaturated (low coating) conditions. The avidity index will only be reported for post baseline visits and if the anti-ePHF IgG antibody response measured on high coating is positive (see definition of positive/negative response in section 8.17.1).

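### For multi-run anti-ePHF IgG samples, the SAP lets the sponsor declare avidity unreportable without a criterion, a named decision-maker, a time or a route that fits the blinding rules

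*SAP*

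**What the plan says.** SAP 7.2 lists among the secondary endpoints: "Determination of the IgG response profile by avidity testing". SAP 8.19 limits when there is a result at all: "The avidity index will only be reported for post baseline visits and if the anti-ePHF IgG antibody response measured on high coating is positive".

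The notes to the assay table in SAP 8.18.1 give two routes to a blank. They begin: "ePHF avidity will not be reported if ePHF IgG is negative or if ePHF IgG average of multiple runs is used". The second route carries a further condition, joined by an underlined conjunction, that "ePHF avidity is considered unreportable by the sponsor". A blanked result gets the status NVR (no valid result) and one of two fixed comments. One comment says that the IgG was negative, the other that it was an average of multiple runs.

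SAP 6.3 sets the firewall: "DATA MUST NEVER BE SENT FROM THE ANALYZING LABORATORIES TO AC IMMUNE SA, THE SITE, BLINDED TEAM MEMBERS". The sponsor is also to have no access to the laboratory files until the study is unblinded after database lock. Under SAP 6.3 and 10.4, however, a semi-unblinded sponsor committee does receive immunogenicity results, after the CRO's unblinded programmer has replaced the subject IDs.

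**The concern.** Whether a result enters a summary should depend on a rule fixed in advance, not on the opinion of a party with an interest in the outcome. The neighbouring assays follow that principle. Anti-CpG and anti-T50 results are positive or negative by a plate-specific cut-point (SAP 8.18.2), and the other titers are classified by fixed threshold factors (SAP 8.18.1). Among the assay rules in SAP 8.18 and 8.19, only avidity depends on a sponsor opinion.

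Protocol 1.4 gives avidity a real job. It is to confirm that the antibodies have the right quality and to support the choice of vaccine for further development. If low values could be dropped, or were more likely to be queried, a group would look better than it is, and a reader of the final tables could not see why the results were lost.

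The second stake is the blind. Because avidity exists only for positive samples, any question about a particular avidity result says that the sample came from a responder.

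**Working it through.** The documents state no sample size, variance, alpha or test for avidity, and SAP 11.6.1 plans no testing of antibody responses. There is no plan figure to reproduce. The check is mainly textual, with two illustrations.

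**1. Scope of the discretion.** It applies only when all of these hold: the visit is post-baseline, anti-ePHF IgG is positive, the IgG value is an average of multiple runs, and the sponsor judges avidity unreportable. It does not reach avidity results in general.

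**2. What is specified.**

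| Element | SAP 8.18.1 |
|---|---|
| Trigger | Average of multiple IgG runs |
| Criterion for unreportable | None |
| Who at the sponsor decides | Not stated |
| When, and whether blinded | Not stated |
| What is recorded | NVR and the multi-run comment only |

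The comment names the assay condition. That a sponsor judgement was made can be inferred, because the rule requires one, but its ground, date and author are not kept. Appendix 2 lists avidity summaries, figures and a listing, but no table of NVR counts.

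**3. Fit with SAP 6.3.** If the decision is made before unblinding, it cannot rest on data sent by the laboratory or on the laboratory files, and the SAP names no other route for it. If it is made after unblinding, treatment may be known. A rule fixed in advance would avoid both difficulties, but none is written.

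**4. Illustration: what a responder signal would reveal.** Initial allocation is 6 active to 2 placebo, so the prior probability of active is 6/8 = 0.75. With assumed positivity rates r on active and f on placebo,

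P(active | positive) = 0.75r / (0.75r + 0.25f).

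- r = 0.30, f = 0.10: 0.225 / (0.225 + 0.025) = 0.90.
- r = 1.00, f = 0.01: 0.75 / (0.75 + 0.0025) = 0.997.

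So the probability would rise from 0.75 to between 0.90 and 0.997 over these assumed ranges, but only for someone who can link the sample to an original subject ID.

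**5. Illustration: what one blank could do.** The values are simulated as independent standard normal (400,000 replicates), and one of n results is removed.

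| Results in group | Lowest removed | One removed at random |
|---|---|---|
| 3 | +0.42 SD | 0 |
| 6 | +0.25 SD | 0 |
| 12 | +0.15 SD | 0 |
| 18 | +0.11 SD | 0 |

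Six is the initial active group. Eighteen (6 + 12) is the active group in a sub-cohort expanded to the protocol maximum. Fewer results will exist where some subjects are negative. The lowest-removed column is the worst case for a single blank.

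**The case against.** The strongest reply is that the clause is narrow and probably technical. Avidity is a ratio of concentrations measured at high and low coating (SAP 8.19). If the IgG value is averaged over several runs, there may be no matched pair from which to form the ratio. A single assay-level ruling on such averages, made without seeing any value, would fit the text. The sponsor's review committee may already see recoded individual avidity profiles at interim analyses (Appendix 2, Figure 14.1.6.2 and Listing 16.2.12.2), so a query under a recoded ID would tell it nothing new about who responded. The missing procedure may be in documents not available here: the committee's charter (SAP 10.4), the separate interim immunogenicity SAP (SAP 10.6) or the blinding plan (Protocol 5.3.8).

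Much of this stands, and it rules out three stronger readings that a reader might infer:

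- **The sponsor decides sample by sample after seeing the value.** The SAP does not say so. The second condition would be redundant if every multi-run sample were blanked, which suggests that some are kept, but a general ruling is also compatible with the wording.
- **The sponsor may never hold laboratory data, so the clause contradicts SAP 6.3.** The ban is on direct transfer from the laboratories and on access to their files before unblinding. Recoded data are expressly allowed.
- **The clause breaks the blind.** Nothing says that the decision-maker sees original IDs.

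The reply does not supply the missing criterion. A technical reason can be written as a technical rule, and then no sponsor opinion is needed.

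**Conclusion.** The point holds in limited form. For positive post-baseline samples with a multi-run IgG average, the SAP as written allows the sponsor to exclude secondary-endpoint results on a ground that is neither defined nor recorded. How that decision fits the firewall in SAP 6.3 is left open. Selective exclusion is permitted, not demonstrated, and a leak of responder status is possible, not shown.

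The size cannot be computed, because the documents do not give the number of multi-run samples or the spread of avidity. The range of about 0.11 to 0.42 SD assumes normal values and loss of the single lowest result in groups of 18 down to 3. Blanking that is unrelated to the value would cause no shift. Because the endpoint is secondary and purely descriptive, this should be corrected before the avidity summaries are relied on, but it does not threaten the primary results.

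**What to change.** In the notes to SAP 8.18.1, delete the reference to the sponsor's judgement and replace it with one fixed assay rule for multi-run averages. For example, report avidity only from a run with a matched, accepted high- and low-coating pair, and otherwise enter NVR. The documents give no run-acceptance limits, so the rule must state them or cite where they are set. The laboratory or the CRO's unblinded team should apply it, without treatment knowledge and without sponsor input.

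In addition:

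- Record the specific ground for each NVR, not only that runs were averaged.
- Report NVR counts by reason, treatment group and visit, next to the avidity summary.
- Where values exist that were already blanked on a sponsor decision, add a sensitivity summary that restores them.
- While editing, correct SAP 8.19, which points to section 8.17.1 for the response definition that stands in 8.18.1.

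The cost is small: wording changes in the SAP and the data-transfer specification, and one or two extra outputs.
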